8.4 Withdrawal of Subjects

A subject should be withdrawn from the study if any of the following occur:

- 1) Withdrawal of subject consent.
- 2) Investigator determines that withdrawal from the study is in the best interest of the subject.
- 3) Major protocol violation (i.e., circumstances where confounding conditions make it impossible to derive sound scientific or medical conclusions from the primary endpoint data generated on a subject).
- 4) Any condition, injury, or disease that becomes apparent during the study and necessitates the termination of the subject from the study; including events detailed in Section 6.3.1- Safety Stopping Rules.
- 5) Administrative reason (e.g., termination of the clinical study by a Regulatory Agency or the Sponsor).

8.5 Subject Withdrawal Procedures

8.5.1 Follow-up Procedures for Subjects Who Withdraw Prematurely

The date and the reason for study drug discontinuation or subject withdrawal from the study must be recorded on the Case Report Form. If the subject has received one or more doses of study

Protocol # COG1201
Version # 3.0 Issue Date 20 Sep 2022

CT1812 in DLB

drug, and has not withdrawn consent, the subject shall return for the Early Termination Visit. The Early Termination Visit will occur within 2 weeks of the last dose.

8.6 Procedures for Replacing Subjects Who Withdraw Prematurely

Subjects who withdraw from the study will not be replaced.

9 TREATMENT PLAN AND METHODS

Approved

Protocol # COG1201
Version # 3.0 Issue Date 20 Sep 2022

CT1812 in DLB

9.1 Table 1, Schedule of Assessments

Approved

Protocol # COG1201

CT1812 in DLB

Version # 3.0 Issue Date 20 Sep 2022

		Visit 1 Screen Day -42 to -1	Visit 2 Baseline Day1	Visit 3 Day 14 (±2)	Visit 4 Day 28 (±2)	Visit 5 Day 42(±2)	Visit 6 Day 56 (±2)	Visit 7 Day 70 (±2)	Visit 8 Day 98 (±2)	Visit 9 Day 126 (±2)	Visit 10 Day 154 (±2)	Visit 11 Early Term Day 182 (±2)	Visit 12 Safety Follow Up Day (210 +2) 30 days post treatment
1	Informed consent	X											
2	Inclusion/Exclusion Criteria	X	X										
3	Demography, Education History, Alcohol and Drug History & Medical History	X											
4	Confirm DLB diagnosis	X											
5	MMSE, GDS	X											
6	ApoE Status	X											
7	Screening laboratories	X											
8	Complete Physical Exam	X	X									X	
9	Brief Physical Exam				X		X		X		X		
10	ECG (12-lead)	X	X		X				X			X	
11	MRI	X											
12	Vital Signs	X	X	X	X	X	X	X	X	X	X	X	X
13	Safety labs (chem, hem, U/A)	X	X	X	X	X	X	X	X	X	X	X	X
14	PK blood sampling		X		X		X		X		X	X	
15	PD plasma biomarkers	X	X		X				X			X	
16	Whole blood sample for future biological research		X										
17	Coagulation testing (PT/INR)	X									X		
18	Optional Lumbar puncture	X										X	
19	Optional CSF biomarkers	X										X	
20	Syn-One Skin Biopsy	X										X	
21	Pregnancy testing and FSH for women that are not surgically sterile	X											
22	C-SSRS	X	X		X		X		X		X	X	X
23	Training on the CDR System (x2)	X											
24	MOCA, CDR** ADCS-ADL, NPI, ADCS-CGIC, MDS-UPDRS Part III		X		X				X			X	
25	CAF, ESS	X	X		X				X			X	
26	Modified Hoehn and Yahr	X											
27	Concomitant Meds	X	X	X	X	X	X	X	X	X	X	X	X
28	Adverse Events assessment		X	X	X	X	X	X	X	X	X	X	X
29	Drug Accountability			X	X	X	X	X	X	X	X	X	
30	Dispense study drug		X		X		X		X		X		
31	Study drug given in clinic with food		X		X		X		X		X	X	

Key for Table 1. Schedule of Assessments

Abbreviations: DLB = Dementia with Lewy Bodies, PROs= Patient Reported Outcomes, MoCA = Montreal Cognitive Assessment Scale, CAF= Clinician Assessment of Fluctuation, ESS = Epworth Sleepiness Scale, MDS-UPDRS part III = Movement Disorder Society – United Parkinson's Disease Rating Scale Part III, ADCS-CGIC = The Alzheimer's Disease Cooperative Study – Clinical Global Impression of Change, ADCS-ADL= The Alzheimer's Disease Cooperative Study - Activities of Daily Living, MMSE = Mini Mental State Exam, CDR= Cognitive Drug Research Battery, ApoE = apolipoprotein E, C-SSRS = Columbia Suicide Severity Rating Scale, ECG=electrocardiogram, GDS = Geriatric Depression Scale, PK=pharmacokinetic, NPI = Neuropsychiatric Inventory

1. Informed consent for subject and caregiver must be obtained prior to the subject undergoing any study-specific procedures.
2. Review of all criteria detailed in Sections 8.2 and 8.3
3. Record demographic information, confirm ethnicity and obtain medical history, drug and alcohol history, and education history.
4. Confirm DLB diagnosis in accordance with criteria based on the 4th report of the DLB Consortium (McKeith et al., 2017). See Appendix B.
5. Perform MMSE and GDS (see sections 11.1.8 and 11.1.7).
6. APOE genetic testing is required for all subjects (see section 9.2.1).
7. Screening labs include viral serology, TSH, FSH (for female subjects that are not surgically sterile) and HbA1c (for diabetic subjects only).
8. Complete physical examination = thorough examination of all body systems (including neurological exam), including height and weight. Weight should be measured on the same scale each time. Height measured only at screening (see section 12.1.2).
9. Brief physical examination = inquire about signs/symptoms, review of general appearance and brief review of body systems, including weight. Weight should be measured on the same scale each time (see section 12.1.2).
10. ECG to be conducted during screening period, and approximately one to two hours post-dose at specified visits (see section 12.1.7).
11. MRI (or CT scan due to contraindication of MRI if approved by medical monitor) performed at screen (if an historical MRI/CT scan is not used) (see section 12.1.8).
12. Vital Signs: body temperature, systolic and diastolic blood pressure, pulse rate and respiration rate
13. Safety labs – Blood Chemistry, Hematology and Urinalysis – Blood should be drawn within an hour of urine collection (see section 12.1.4).
14. Collect PK samples. See Section (see section 10.2) for timing of sample collection. See Laboratory Procedures Manual for sample handling.
15. Collect PD plasma biomarker samples. See Section (see section 10.2) for timing of sample collection. See Laboratory Procedures Manual for sample handling. If the PD sample cannot be collected prior to dosing on Day 1 baseline, the subject may not receive the first dose of study drug. Dosing will be delayed until this successful collection of this pre-dose baseline sample.
16. Whole blood sample collected for future biologic research (see section 10) See Laboratory Procedures Manual for sample handling
17. Coagulation testing includes prothrombin time (PT) and INR (see section 12.1.4).
18. Optional lumbar puncture: For subjects opting to undergo lumbar puncture, the procedure should be performed at least 24 hours before the Baseline visit and again at Day 182 (the end of the dosing period). LP on the Day 182 visit should be performed within t-e – 2-day visit window minimally 24 hours prior to the Day 182 visit procedures (e.g., Day 181) and prior to dosing on that day (see section 10.3).

19. If adequate volume is available, CSF will be stored for future evaluation of biomarkers of target engagement or disease modification. See Laboratory Procedures Manual for sample handling (see section 10.3)
CSF should be sent for cell counts, if such testing is available (white blood cells and red blood cells, with differential if either of the counts is abnormal), CSF protein, and CSF glucose at Screening and Day 182. If abnormalities are observed at Screening, they should be discussed with the medical monitor before randomizing the subject.
20. Subjects will undergo Syn-One Test™ punch biopsy during the screening period once all other screening procedures are complete with this procedure to occur at least 24 hours before the Baseline visit.
21. Pregnancy testing for female subjects that are not surgically sterile (see section 12.1.6)
22. C-SSRS Screening/Baseline version used at screening visit, Since Last Visit version used at all other visits and will be administered prior to dosing (see section 11.1.12).
23. The CDR system requires two training sessions to be conducted at least 30 minutes apart during the screening period. These trainings can be done at the screening visit or scheduled on separate days during the screening period.
24. The PROs/assessments will all be completed prior to dosing and procedures during the study visit (see section 11.1).
25. The CAF and ESS will be administered prior to dosing and procedures during the study visit (see section 11.1.2 and 11.1.3).
26. The Modified Hoehn and Yahr will be administered at screening prior to other procedures (see section 11.1.1).
27. All concomitant medications will be recorded from screening through Day 210 (see section 9.3).
28. During Screening (post-consent), only SAEs related to a study-specific procedure will be collected. For all related AEs of moderate or severe intensity ongoing at the end of the study, follow-up will continue until the event has resolved to baseline severity, the event is assessed as stable by the Investigator, or the patient is lost to follow-up or the patient withdraws consent (see section 12).
29. Drug accountability must be performed at each visit with the exception of screening, baseline and day 210 (safety follow up) (see section 6.4).
30. Where drug is dispensed, the remainder of the previous bottle should be collected and retained by the site.
31. Study drug should be administered in clinic with food.

9.2 Visit Specific Procedures

9.2.1 Visit 1 / Screening

The Screening visit must be performed within 42 days prior to Day 1 – Baseline. The following procedures will be performed at the Screening visit:

- Subjects or their Legally Authorized Representative (LAR) (or designee as applicable by local law) must provide written informed consent to the study procedures prior to any study procedures. The caregiver must also provide written informed consent at this time.
- Evaluate subject eligibility against study inclusion/exclusion criteria.
- Confirm DLB diagnosis (see section Appendix B).
- Record demographic information, confirm ethnicity, alcohol and drug history, educational history and obtain medical history.
- Administer the Mini-Mental State Exam (MMSE) and Geriatric Depression Scale (GDS)
- Administer Modified Hoehn and Yahr
- Administer CAF and ESS
- Administer C-SSRS Screening/Baseline version
- Perform complete physical examination with neurological examination
- Measure and record vital signs
- Perform 12-lead ECG
- MRI (or CT scan due to contraindication of MRI, if approved by medical monitor), unless an historical MRI/CT scan is used.
- Draw blood and prepare samples for APOE status. Apolipoprotein E (ApoE) genotype is associated with the risk and age of onset of DLB. Blood samples (approximately 10 mL) to perform this testing will be collected and will be utilized to further understanding of response to CT1812. The genotyping is mandatory for participation in the study and the results will not be revealed to either the investigator or subject and caregiver.
- Draw blood and prepare samples for coagulation testing (PT/INR), serum chemistry, hematology, viral serology, TSH, FSH (in women who had their last natural menses less than 24 months prior to screening and who are not surgically sterile) and HbA1c (in known

diabetics), Blood should be drawn within an hour of urine collection. Abnormal results at screening will exclude a subject unless the investigator is aware of a specific reason that can explain the abnormality (e.g., elevated CPK 24 hours after strenuous exercise). Should an abnormal lab remain abnormal on repeat the subject will be excluded. Collect blood sample for exploratory biomarker samples

- Collect blood samples for exploratory plasma biomarker analysis
- Collect urine sample for β -HCG pregnancy test for women who are not postmenopausal (last natural menses was less than 24 months ago) that are not surgically sterile.
- Collect urine sample for urinalysis
- Record concomitant medications
- Once all above screening assessments are completed, complete the subject eligibility form located in the study manual and submit to the medical monitor.
- If a subject opts in to the lumbar puncture, the subject should undergo the lumbar puncture (CSF biomarkers to be collected during this procedure) at least 24 hours before the Baseline visit.
- Once all other screening activities are complete, the subject should undergo the Syn-One Test™ skin biopsy at least 24 hours prior to the baseline visit.
- During the screening period, subjects will need to be trained on how to use the CDR system. This is an automated battery amenable to measurement of cognitive deficits in patients with DLB (McKeith et al. 2000; Wesnes et al. 2014). It consists of 10 performance tasks measuring attention, working memory, episodic memory, and executive function, performed by the patient on a laptop. Two training sessions need to be conducted at least 30 minutes apart during the screening period to allow patients to become familiar with the procedure, reduce test anxiety, reduce learning effects, and produce a stable baseline. These trainings can be done at the screening visit or scheduled on separate days during the screening period.
- If eligible, schedule subject to return to the clinic on Day 1 to initiate CT1812 dosing.

9.2.2 Visit 2 / Study Day 1 – Baseline

The following procedures will be conducted on Day 1:

Pre-dose Assessments:

- Confirm continued eligibility prior to dosing.
- Administer MOCA, CDR, ADCS-ADL, NPI, ADCS-CGIC, MDS-UPDRS Part III, CAF and ESS
- Administer C-SSRS Since Last Visit version
- Perform complete physical examination with neurological examination
- Measure and record vital signs
- Draw blood and prepare sample for serum chemistry and hematology Blood should be drawn within an hour of urine collection.
- Collect whole blood sample for future biomedical research including potential genetic analyses
- Collect blood samples for PK and exploratory plasma biomarker analysis
- Collect urine samples for urinalysis
- Record any new medical conditions, AEs, or changes in medications since the Screening visit.
- Administer study drug with food.

Post-dose Assessments

- Record ECG ~1- 2 hours post-dose
- Dispense study drug supply and instructions for at home dosing.
- Instruct subject to return for Day 14 visit including instructions to bring study drug to the Day 14 visit

9.2.3 Visit 3 Study Day 14

The subject will return to the clinic for the following assessments:

- Measure and record vital signs
- Draw blood and prepare sample for serum chemistry and hematology. Blood should be drawn within an hour of urine collection.
- Collect urine samples for urinalysis,
- Record any AEs.
- Record changes in medications.
- Conduct drug accountability, return study drug to the subject for continued dosing
- Instruct subject to return for Day 28 visit including instructions to hold dose on morning of Day 28 visit and to bring study drug with them

9.2.4 Visit 4 Study Day 28

The subject will return to the clinic for the following assessments:

Pre-dose Assessments:

- Administer MOCA, CDR, ADCS-ADL, NPI, ADCS-CGIC, MDS-UPDRS Part III, CAF and ESS
- Administer C-SSRS Since Last Visit version
- Perform brief physical examination
- Measure and record vital signs
- Draw blood and prepare sample for serum chemistry and hematology.) Blood should be drawn within an hour of urine collection
- Collect blood samples for PK and exploratory plasma biomarker analysis

- Collect urine samples for urinalysis
- Record any AEs.
- Record changes in medications.
- Conduct drug accountability
- Collect remaining drug in old bottle.
- Administer Day 28 dose with food.

Post-dose Assessments:

- Record ECG ~1- 2 hours post -dose).
- Dispense study drug supply and instructions for at home dosing
- Instruct subject to return for Day 42 visit including instructions to bring study drug with them to the Day 42 visit

9.2.5 Visit 5 Subject Day 42

The subject will return to the clinic for the following assessments:

- Measure and record vital signs
- Draw blood and prepare sample for serum chemistry and Blood should be drawn within an hour of urine collection.
- Collect urine samples for urinalysis
- Record any AEs.
- Record changes in medications.
- Conduct drug accountability, return study drug to the subject for continued dosing
- Instruct subject to return for Day 56 visit including instructions to hold dose on morning of Day 56 visit and to bring study drug with them

9.2.6 Visit 6 Study Day 56

The subject will return to the clinic.

Pre-dose Assessments:

- Administer C-SSRS Since Last Visit version
- Perform brief physical examination
- Measure and record vital signs
- Draw blood and prepare sample for serum chemistry and hematology Blood should be drawn within an hour of urine collection.
- Collect blood samples for PK
- Collect urine samples for urinalysis
- Record any AEs.
- Record changes in medications.
- Conduct drug accountability
- Administer Day 56 dose with food.

Post-dose Assessments:

- Dispense study drug supply and instructions for at home dosing
- Instruct subject to return for Day 70 visit including instructions to bring study drug with them to the Day 70 visit

9.2.7 Visit 7 Study Day 70

The subject will return to the clinic for the following assessments:

- Measure and record vital signs
- Draw blood and prepare sample for serum chemistry and hematology Blood should be drawn within an hour of urine collection.

- Collect urine samples for urinalysis
- Record any AEs.
- Record changes in medications.
- Conduct drug accountability, return study drug to the subject for continued dosing
- Instruct subject to return for Day 98 visit including instructions to hold dose on morning of Day 98 visit and to bring study drug with them

9.2.8 Visit 8 Study Day 98

The subject will return to the clinic.

Pre-dose Assessments:

- Administer MOCA, CDR, ADCS-ADL, NPI, ADCS-CGIC, MDS-UPDRS Part III, CAF and ESS
- Administer C-SSRS Since Last Visit version
- Perform brief physical examination
- Measure and record vital signs
- Draw blood and prepare sample for serum chemistry and hematology. Blood should be drawn within an hour of urine collection.
- Collect blood samples for PK and exploratory plasma biomarker analysis
- Collect urine samples for urinalysis
- Record any AEs
- Record changes in medications
- Conduct drug accountability
- Collect any remaining drug in old bottle

- Administer Day 98 dose with food

Post-dose Assessments:

- Record ECG ~1- 2 hours post-dose
- Dispense study drug supply and instructions for at home dosing
- Instruct subject to return for the Day 126 Study Visit

9.2.9 Visit 9 Study Day 126

The subject will return to the clinic for the following assessments:

- Measure and record vital signs
- Draw blood and prepare sample for serum chemistry and hematology Blood should be drawn within an hour of urine collection.
- Collect urine samples for urinalysis
- Record any AEs
- Record changes in medications
- Conduct drug accountability, return study drug to the subject for continued dosing
- Instruct subject to return for Day 154 visit including instructions to hold dose on morning of Day 154 visit and to bring study drug with them

9.2.10 Visit 10 Study Day 154

The subject will return to the clinic.

Pre-dose Assessments:

- Administer C-SSRS Since Last Visit version
- Perform brief physical examination
- Measure and record vital signs

- Draw blood and prepare sample for serum chemistry and hematology. Blood should be drawn within an hour of urine collection
- Draw blood for coagulation testing
- Collect blood samples for PK
- Collect urine samples for urinalysis
- Record any AEs
- Record changes in medications
- Conduct drug accountability
- Administer Day 154 dose with food

Post-dose Assessments:

- Dispense study drug supply and instructions for at home dosing
- Instruct subject to return for the relevant Day 182 Study Visit Including instructions to hold dose on morning of next visit and to bring remaining study drug with them

9.2.11 Visit 11 Study Day 182 / Early Termination

The subject will return to the clinic.

- Within the -2-day window for scheduling assessments:
- If the subject opted into the lumbar puncture, perform lumbar puncture, and collect CSF a minimum of 24 hours before the Day 182 / Early Termination Visit
- The subject should undergo the Syn-One Test™ skin biopsy at least 24 hours prior to the Day 182 / Early Termination Visit

Pre-dose Assessments:

- Administer MOCA, CDR, ADCS-ADL, NPI, ADCS-CGIC, MDS-UPDRS Part III, CAF and ESS
- Administer C-SSRS Since Last Visit version

- Perform complete physical examination with neurological examination
- Measure and record vital signs
- Draw blood and prepare sample for serum chemistry and hematology. Blood should be drawn within an hour of urine collection.
- Collect blood samples for PK and exploratory biomarker analysis
- Collect urine samples for urinalysis
- Record any AEs
- Record changes in medications
- Conduct drug accountability) and collect all remaining drug from subject
- Administer last dose of study drug with food

Post-dose Assessments

- Record ECG ~1-2 hours post-dose
- Instruct subject to return for Day 210, safety follow up visit

Any subject that discontinues prematurely should complete Visit 11/Day 182 as an Early Termination visit. For subjects prematurely discontinuing, an early termination visit should be scheduled within 2 weeks of the last dose of study medication. If early termination visit is 3 or more days from the last dose, PK sampling should not be done. The remainder of the assessments below should be performed.

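### The shared Day 182 / Early Termination visit lists an in-clinic dose, with no exception for subjects stopped under the liver rule in Protocol 6.3.1

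*Protocol*

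**What the plan says.** Protocol 9.2.11 covers Day 182 and Early Termination under one heading and one list. The list contains "Administer last dose of study drug with food", printed in the pre-dose block, and then "Record ECG ~1-2 hours post-dose". Below the list it says: "Any subject that discontinues prematurely should complete Visit 11/Day 182 as an Early Termination visit". One exemption follows: "If early termination visit is 3 or more days from the last dose, PK sampling should not be done". The section then adds: "The remainder of the assessments below should be performed".

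Table 1 (Protocol 9.1) has the same structure. The column is headed "Visit 11 Early Term Day 182", and row 31, "Study drug given in clinic with food", is marked in it. Footnote 31 reads "Study drug should be administered in clinic with food" and names no exception. Footnote 10 times the on-study ECGs from the dose.

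Protocol 6.3.1, repeated in the synopsis, sets three liver criteria:
- ALT or AST above 5 x ULN;
- ALT or AST above 3 x ULN with raised bilirubin or INR;
- ALT or AST above 3 x ULN with listed symptoms or eosinophilia.

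A subject who meets any of them is to get no more study drug. Restart is possible only if a reversible cause is found, the liver tests have normalized, and the site investigator and Medical Monitor have discussed it.

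**The concern.** The subjects whom 6.3.1 takes off drug are the ones that the withdrawal sections send to a visit whose checklist includes a dose. A coordinator working from 9.2.11 or Table 1 finds an exemption for PK sampling and none for dosing.

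What is at stake is subject safety. Protocol 3.3 reports liver-test elevations in earlier CT1812 studies, including an ALT of 4.7 x ULN at 560 mg that returned to normal once the drug was stopped. Section 6.3.1 puts conditions on any restart, and the visit list carries none of them.

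The ECG has a related gap. If no dose is given, an instruction to record it one to two hours after the dose has no reference time.

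**Working it through.** The plan gives no figure to reproduce. The check follows one subject through the sections in order.

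1. **Stopped.** The subject meets a 6.3.1 liver criterion, so no further drug is allowed.
2. **Withdrawn.** Protocol 8.4, item 4, names 6.3.1 events among the reasons for withdrawal.
3. **Sent to the visit.** Protocol 8.5.1 requires any subject who has been dosed and has not withdrawn consent to attend the Early Termination visit, no later than two weeks after dosing ended.
4. **Given the list.** Protocol 9.2.11 makes that visit Visit 11, and Visit 11 lists a dose. Row 31 of Table 1 agrees.
5. **Exceptions searched for.** In 9.2.11, only PK sampling is exempted. In footnote 31, nothing is. In footnote 10, the ECG has no alternative timing.

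Steps 1 and 4 give opposite instructions for the same subject, and no cross-reference at the visit says which prevails.

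**The listed dose.** Protocol 6.3 sets a daily dose of 2 capsules, and 6.1 supplies 50 mg or 150 mg capsules. The dose is 2 x 50 = 100 mg or 2 x 150 = 300 mg in the active arms.

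**Timing against the liver rechecks.** Section 6.3.1 asks for a repeat by day 4 after stopping and, if values are still raised, another 4 days later with a 1-day margin: 4 + 4 - 1 = 7 to 4 + 4 + 1 = 9, so days 7 to 9. The visit may fall on any day up to 14. It can therefore come before, between or after the rechecks, and the schedule does not ensure that liver tests have normalized by then.

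**Effect on the efficacy analyses.** None. The list places the efficacy scales before the dose. SAP 10.4 only lists Early Termination data from before study Day 170.

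**The case against.** The strongest reply is that 6.3.1 already answers the question. It is a categorical bar specific to these subjects, and a general visit checklist does not override it. A reader might infer from 9.2.11 that the protocol directs sites to re-dose liver-stopped subjects, or that nothing cancels the dose. The documents do not support that: for these subjects 6.3.1 cancels it. What is missing is the exception at the place where the visit is carried out.

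Other text points the same way:
- Timing the visit from the end of dosing, and the PK exemption at three or more days, both presume that the subject is already off drug.
- The list also books the Day 210 visit, which the synopsis and 5.3 provide for subjects who complete through Day 182. It was evidently written for completers.
- The sentence on the remainder speaks of assessments below, while the dose line is above it. It is ambiguous and should not be read as plainly including the dose. The conflict does not need it, because the instruction to complete Visit 11 is enough.
- Under 6.3, clinic doses are taken on staff instruction, and Table 1 dispenses no drug at Visit 11.

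All of this stands, and it lowers the chance that a dose would be given. None of it is a written exception in 9.2.11, Table 1 or footnote 31, and up to about 30 sites would each have to resolve the conflict themselves.

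**Conclusion.** The conflict is real and should be corrected as a minor safety point. The printed visit schedule disagrees with the controlling liver rule. Followed literally, it would give one daily dose to a subject whom the protocol forbids to dose. This rests on reading row 31 and the dose line as applying to the whole combined column, as they are printed. It also assumes that sites would most likely follow 6.3.1.

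The size cannot be stated beyond that one dose per subject. The documents do not say how many subjects would be stopped under 6.3.1 and attend this visit. A reader might look for a rate in the liver-related withdrawals that Protocol 3.3 reports for COG0105. Those events were mild and are not shown to meet the 6.3.1 criteria, so they do not estimate it. Nor does the plasma half-life in 3.3 say anything about how likely a dose is.

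**What to change.** - **9.2.11 and Table 1 footnote 31:** state that the in-clinic dose applies to Day 182 completers only and that no study drug is given at an Early Termination visit. The minimum that the conflict requires is no drug for any subject stopped under 6.3.1. The wider wording is simpler for sites and fits a visit that is timed from the end of dosing.
- **9.2.11 and Table 1 footnote 10:** state that the ECG at an Early Termination visit is recorded without reference to a dose.

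The cost is wording: no extra subjects, visits or tests, and no SAP change. The sponsor would need to classify the amendment under Protocol 16.1.1, which treats a change as administrative only if it has no impact on subject safety or the science. It could be combined with the next amendment.
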